1.0 OBJECTIVES

Primary objective:

Response rate (CR conversion to MRD negative, PR conversion to nPR or CR, and nPR conversion to CR) with ofatumumab treatment in patients with residual disease.

Secondary objectives:

1. Determine the time-to-treatment failure and progression-free survival
2. Determine the time-to-next CLL/SLL treatment after ofatumumab
3. Evaluate the safety and tolerability of ofatumumab for residual disease
4. Evaluate pharmacokinetics of ofatumumab in this trial for residual disease and in maintenance

2.0 BACKGROUND

Rationale:

Ofatumumab has significant single-agent activity in treating patients with CLL refractory to fludarabine and alemtuzumab (FA-ref) and fludarabine-refractory patients with bulky (>5cm) lymph nodes (BF-ref), as demonstrated by the interim analysis of the pivotal trial¹. The overall response (OR) rate for FA-ref (n=59) and BF-ref (n=79) was 58% and 47%, respectively. The median time to response was 1.8 months and median response duration for both populations was 6 months. Treatment with ofatumumab was very well tolerated. In addition, a phase I/II trial of single-agent ofatumumab in relapsed patients with CLL demonstrated an ORR of 50% in the 26 patients treated with ofatumumab 300 mg followed by 3 weekly doses of 2000 mg (4 total doses)². This treatment was well tolerated with the most common side effect being infusion-related reactions. This human monoclonal antibody against CD20 binds to a unique epitope composed of the small- and large-loop domains of CD20 and is highly effective at fixing complement for complement-dependent cytotoxicity (CDC). *In vitro* studies demonstrated higher levels of CDC against primary CLL cells with ofatumumab compared to rituximab, especially with cells with low CD20 antigen density^{3,4}.

Alemtuzumab is a monoclonal antibody against CD52, approved by FDA for treatment of untreated and previously treated patients with CLL. CD52 is also present on normal T, B and NK cells; therefore these normal cells are also at risk for elimination with alemtuzumab treatment. Alemtuzumab is highly effective at eliminating CLL from blood and bone marrow, the usual site of residual disease after purine analogue-based treatment. Several Phase II trials have been conducted to evaluate the efficacy of alemtuzumab at eliminating residual disease and treatment of minimal residual disease (MRD)⁵⁻¹⁰. While these studies that have clearly demonstrated the ability of alemtuzumab to eliminate MRD, both the safety and clinical relevance of this strategy are debated. In fact, 2 trials were terminated early owing to alemtuzumab-related infection complications with opportunistic organisms^{8,10}. One of these studies demonstrated prolonged progression-free survival in patients treated with alemtuzumab⁸, the other trial did not show any benefit with alemtuzumab¹⁰. Therefore

this strategy with alemtuzumab remains investigational and requires further clinical trial to optimize and address safety issues.

Chemoimmunotherapy (CIT) regimens, particularly fludarabine combined with cyclophosphamide and rituximab, the monoclonal antibody against CD20, are highly effective treatment for patients with CLL both frontline (CLL8)¹¹ and relapsed (REACH trial)¹² patients. Despite the effectiveness of this combination, many of frontline and the majority of salvage patients have residual disease present following the standard 6 cycles of FCR treatment, demonstrated by the highly sensitive 4-color flow cytometry assay done on bone marrow^{13,14}. Given the high affinity of ofatumumab for CD20, highly efficient CDC, and clinical activity in FA-ref and BF-ref patients, it is an ideal antibody to treat residual disease following CIT and for maintenance. Participants in this trial will have residual disease following chemotherapy or CIT with leukemia cells expressing CD20.

Ofatumumab is an attractive option for clinical trial to treat residual disease and for maintenance in patients with CLL. CD20 is present on CLL and normal B cells, but not on T cells. Therefore, the potential for immune suppression with ofatumumab is much less than that seen with alemtuzumab. This has been confirmed also in clinical trials. In patients with residual disease, in order to be eligible for this trial, their CLL cells must express CD20, thereby providing a target for ofatumumab. The overall primary objective of this phase II trial is to evaluate the activity (response rate) of ofatumumab in treating residual disease in patients with CLL/SLL who have been treated with chemotherapy or chemoimmunotherapy (CIT) containing rituximab or ofatumumab and who have detectable residual leukemia cells expressing CD20 post-treatment.

Patients will be enrolled in 1 of 2 cohorts as follows:

1. Complete responders with evidence of minimal residual disease by 4-color flow cytometry.
2. Partial (PR) and nodular partial (nPR) responders with evidence of residual disease.

Ofatumumab is currently under development by GlaxoSmithKline and Genmab for the treatment of relapsed or refractory B-cell follicular lymphoma (FL) for previously untreated FL, for the treatment of relapsed or refractory B-cell chronic lymphocytic leukemia (CLL), for previously untreated CLL and for the treatment of active rheumatoid arthritis and other related autoimmune diseases.

3.0 BACKGROUND DRUG INFORMATION

Ofatumumab FDA-Labeled Indication: refractory chronic lymphoid leukemia

US Trade Name: Arzerra

Dosing & Indications:

How Supplied: Intravenous solution, 20 mg/mL

*Adult Single-Agent Dosing (This dosing schedule refers to the pivotal trial. Please refer to **Section 5.0 Treatment Plan** for the dosing schedule in this trial).*

- Refractory chronic lymphoid leukemia: 300 mg IV, followed 1 week later by 2000 mg IV weekly for 7 doses (dose 2 to 8), followed 4 weeks later by 2000 mg every 4 weeks for 4 doses (dose 9 to 12); premedicate 30 min to 2 hr before each dose with acetaminophen (1000 mg or equivalent), oral or IV antihistamine (cetirizine 10 mg or equivalent), and IV corticosteroid (prednisolone 100 mg or equivalent).
 - Corticosteroid premedication dose may be gradually reduced for doses 3 through 8, if grade 3 or greater infusion reaction did not occur with the preceding dose.
 - Corticosteroid premedication dose may be reduced to prednisolone 50 to 100 mg or equivalent for doses 10 through 12, if grade 3 or greater infusion reaction did not occur with dose 9.
 - Initiate dose 1 at an initial rate of 12 mL/hr (3.6 mg/hr), if infusion is well-tolerated, rate may be escalated in 2-fold increments at 30 min intervals to a maximum of 200 mL/hr.
 - Initiate dose 2 at an initial rate of 12 mL/hr (24 mg/hr), if infusion is well-tolerated, rate may be escalated in 2-fold increments at 30 min intervals to a maximum of 200 mL/hr
 - Initiate (dose 3 through 12) at an initial rate of 25 mL/hr (50 mg/hr), if infusion is well-tolerated, rate may be escalated in 2-fold increments at 30 min intervals to a maximum of 400 mL/hr

Mechanism of Action/Pharmacokinetics:

Mechanism of Action

Ofatumumab is a human IgG1-kappa monoclonal antibody that binds to the CD20 molecule on normal B lymphocytes and on B-cell chronic lymphocytic leukemia, resulting in B-cell lysis.

Pharmacokinetics (single-agent refractory CLL/SLL patient population)

- Distribution: 1.7 to 5.1 L
- Excretion: total body clearance, mean: 0.01 L/hr
- Elimination half life: approximately 14 days

Administration/Monitoring:

Administration

Intravenous

- Do NOT shake, mix by gentle inversion.
- Do NOT mix ofatumumab with other drugs.
- Colorless solution with small amounts of visible, translucent-to-white, amorphous, ofatumumab particles is normal; do not use if discolored, cloudy, or if foreign particulate matter is present.

- Total volume of prepared solution should be 1000 mL; withdraw appropriate volume of 0.9% sodium chloride solution to accommodate volume of ofatumumab.
- Do NOT administer as an intravenous push or bolus.
- Do NOT administer ofatumumab with other drugs.
- Administer with an infusion pump, the in-line filter supplied with product, and polyvinyl chloride administration sets.
- Infusion should be started within 12 hr of preparation; discard prepared solution after 24.
- Initiate dose 1 at an initial rate of 12 mL/hr (3.6 mg/hr), if infusion is well-tolerated, rate may be escalated in 2-fold increments at 30 min intervals to a maximum of 200 mL/hr.
- Initiate dose 2 at an initial rate of 12 mL/hr (24 mg/hr), if infusion is well-tolerated, rate may be escalated in 2-fold increments at 30 min intervals to a maximum of 200 mL/hr.
- Initiate dose 3 through 12 at an initial rate of 25 mL/hr (50 mg/hr), if infusion is well-tolerated, rate may be escalated in 2-fold increments at 30 min intervals to a maximum of 400 mL/hr.

Monitoring

- Evidence of tumor response is indicative of efficacy.
- CBC regularly, including platelet count and differential.
- CBC more frequently in patients who develop grade 3 or 4 cytopenias, including platelet count and differential.
- Hepatitis B virus (HBV) infection; clinical and laboratory screening before initiation of therapy for those at high risk of HBV infection; hepatitis B carriers, signs of active HBV for 6 to 12 months after therapy.
- Infusion reaction (bronchospasm, dyspnea, laryngeal edema, pulmonary edema, flushing, hypertension, hypotension, syncope, cardiac ischemia/infarction, back pain, abdominal pain, pyrexia, rash, urticaria, and angioedema), especially with first 2 infusions.

Dose Adjustments:

- body weight: no dose adjustment is recommended
- gender: no dose adjustment is recommended
- infusion reaction, grade 1 or 2: interrupt infusion and if reaction resolves or remains less than or equal to grade 2, resume at one-half the previous infusion rate; resume infusion at normal infusion rate as tolerated
- infusion reaction, grade 3: interrupt infusion and if reaction resolves or remains less than or equal to grade 2, resume infusion at a rate of 12 mL/hr; resume infusion at normal infusion rate as tolerated
- infusion reaction, grade 4: discontinue the infusion and do not resume

Contraindications:

- Specific contraindications have not been determined

Precautions:

- Chronic obstructive pulmonary disease, moderate to severe (unapproved use); risk of grade 3 bronchospasm during infusion.
- Cytopenias, including prolonged severe neutropenia and thrombocytopenia may occur; monitoring recommended.
- Hepatitis B infection, carriers or at risk of infection; risk of hepatitis B reactivation with fulminant hepatitis, hepatic failure, and death; evaluate for evidence of infection before beginning treatment and closely monitor for reactivation for 6 to 12 months following therapy; discontinue therapy if viral hepatitis occurs.
- Infusion reactions, some serious (eg. bronchospasm, dyspnea, laryngeal edema, pulmonary edema, angioedema, cardiac ischemia/infarction) have been reported; especially during first 2 infusions; premedication is recommended; depending on the severity of the reaction, adjustment in infusion rate, interruption, and/or discontinuation of therapy is recommended.
- Obstruction of small intestinal may occur.
- Progressive multifocal leukoencephalopathy (PML) including fatalities, may occur; new onset or changes in preexisting neurological signs and symptoms may be indicative of PML; discontinue therapy if PML occurs.
- Viral vaccination, live; do not use in patients who recently received ofatumumab therapy.

Potential Side Effects:

Common

- Dermatologic: rash (all grades, 14% to 17%; grade 3 or greater, less than 1% to 2%)
- Gastrointestinal: diarrhea (18% to 19%), nausea (11% to 12%)
- Hematologic: anemia (all grades, 16% to 17%; grade 3 or greater, 5% to 8%)
- Respiratory: bronchitis (all grades, 11% to 19%; grade 3 or greater, less than 1% to 2%), cough (19%), dyspnea (all grades, 14% to 19%; grade 3 or greater, 2% to 5%), pneumonia (all grades, 23% to 25%; grade 3 or greater, 14% to 15%), upper respiratory infection (3% to 11%)
- Other: fatigue (15%), Fever (all grades, 20% to 25%; grade 3 or greater, 3% to 5%)

Serious

- Gastrointestinal: bowel obstruction
- Hematologic: neutropenia, Grade 3 or greater (42%)
- Hepatic: relapsing type B viral hepatitis
- Immunologic: infectious disease (all grades, 70%; grade 3 or greater, 29%), sepsis (all grades, 8% to 10%; grade 3 or greater, 8% to 10%)
- Neurologic: progressive multifocal leukoencephalopathy
- Other: complication of infusion (first infusion, 44%; second infusion, 29%)

Unused and Expired Study Drug:

Expired ofatumumab and ofatumumab left unused upon completion of the study will be destroyed and dispensed of by the MD Anderson Cancer Investigational Pharmacy.

4.0 PATIENT ELIGIBILITY

4.1 Inclusion criteria:

1. Diagnosis of CD20⁺ chronic lymphocytic leukemia (CLL) or small lymphocytic lymphoma (SLL) treated with chemotherapy or chemoimmunotherapy:
 - Post-frontline therapy, patients must have non-progressing disease and be 4 mo to 1 yr post treatment
 - Post-treatment for relapsed CLL/SLL, eligible patients must have non-progressing disease and be 3 mo to 1 yr post treatment
2. Patients (CR, nPR, or PR at enrollment) must have measurable disease, which may include MRD by 4-color flow cytometry
3. Adequate renal and hepatic function (creatinine <2mg/dL, bilirubin <2mg/dL). Patients with renal or liver dysfunction due to organ infiltration by lymphocytes may be eligible after discussion with the study chairman. Patients with Gilbert's syndrome are eligible.
4. Age ≥ 18 years
5. ECOG performance status of 0-2
6. Provide informed consent indicating patient is aware of the investigational nature of this study according to the policies of the MDACC IRB
7. Patients of childbearing potential (females who have not been postmenopausal for at least 12 consecutive months or who have not undergone previous surgical sterilization or males who have not been surgically sterilized) must be willing to practice birth control during the study.

4.2 Exclusion criteria:

1. Positive serology for Hepatitis B virus (HB) defined as a positive test for HBsAg. In addition, if negative for HBsAg but HBcAb positive (regardless of HBsAb status), a HB DNA test will be performed and if positive the subject will be excluded
2. Concurrent chemotherapy, radiotherapy, or immunotherapy, including other monoclonal antibodies. Localized radiotherapy to an area not compromising bone marrow function does not apply
3. Active infection or significant medical illness, including current active hepatic or biliary disease (with exception of patients with asymptomatic gallstones, liver involved with CLL/SLL or stable chronic liver disease per investigator assessment)
4. Pregnant and breastfeeding women are excluded.

5.0 TREATMENT PLAN

This is a single-arm, open label trial of ofatumumab. Treatment with ofatumumab will be 300 mg dose 1, then 1,000 mg weekly x 7 (referred to as "treatment"), then 1,000 mg every 2 months beginning on week 12 for a total of 2 years of treatment or until progression (referred to as "maintenance"). The "follow-up" period will be the period after completion of "maintenance".

Ofatumumab pre-medication must be given within 30 minutes to 2 hours prior to each infusion:

Table 1. Recommended Pre-medication Prior to Ofatumumab Infusions

Infusion #	Acetaminophen (po) or equivalent	Antihistamine (iv or po) diphenhydramine or equivalent	Glucocorticoid (iv) prednisolone or equivalent
1 st	1000 mg	50 mg	50 mg
2 nd	1000 mg	50 mg	50 mg
3 rd -N th	1000 mg	50 mg	0 – 50 mg ¹

1. If the 2nd infusion was completed without the patient experiencing any grade 3 AE, pre-medication with corticosteroid may be reduced or omitted before the 3rd to Nth infusion at the discretion of the investigator.

First Infusion of 300 mg and 1000 mg Ofatumumab

The first dose administered of ofatumumab should be 300 mg to minimize infusion reactions. The initial rate of the **300 mg** (0.3 mg/ml) and first **1000 mg** (1.0 mg/ml) ofatumumab doses should be 12mL/hr. If no infusion reactions occur the infusion rate should be increased every 30 minutes according to Table 2, to a maximum of 200 mL/hr.

Table 2. Infusion Rate at 1st and 2nd Ofatumumab Infusion

Time	mL/hour
0 – 30 minutes	12
31 – 60 minutes	25
61 – 90 minutes	50
91 – 120 minutes	100
121 – 150 + minutes	200

If an infusion reaction develops, the infusion should be temporarily slowed or interrupted. Additional corticosteroids may be given at the discretion of the treating physician. Upon restarting, the infusion rate should be half of the infusion rate at the time the infusion was paused. If, however, the infusion rate was 12 mL/hour before the pause, the infusion should be restarted at 12 mL/hour. Hereafter, the infusion rate may be increased according to the judgment of the investigator, in the manner described in this section.

Subsequent Infusions of 1000 mg Ofatumumab

If the previous infusion was completed without any grade ≥ 3 infusion-associated AE, the subsequent infusion of ofatumumab 1000mg (1.0mg/mL) can start at a rate of 25 mL/hour and should be doubled every 30 minutes up to a maximum of 400 mL/hr, according to

Table 3. The duration of the infusion will be approximately 4 hours if this schedule is followed. If the previous infusion was completed with any grade ≥ 3 infusion associated AE, the subsequent infusion should start at a rate of 12 mL/hour according to Table 2.

Table 3. Infusion Rate for Ofatumumab Infusions 3 and beyond

Time	mL/hour
0 – 30 minutes	25
31 – 60 minutes	50
61 – 90 minutes	100
91 – 120 minutes	200
121+ minutes	400

During infusion the patient should be monitored closely and appropriate measurements should be performed whenever judged necessary.

There are no proposed or planned ofatumumab dose reductions for toxicities. Toxicities will be addressed by escalating premedication, slowing the infusion rate, or delaying planned dose as determined by the treating physician.

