9.0 REMOVAL FROM STUDY

9.1 Progressive or Relapsed Disease

Progressive disease (PD) will be characterized by at least one of the following:

- a. $\geq 50\%$ increase in the sum of the products of at least two nodes or appearance of new palpable lymph nodes on two consecutive examinations two weeks apart (at least one node must be ≥ 2 cm).
- b. $\geq 50\%$ increase in the size of liver and/or spleen as determined by measurement below the respective costal margin; appearance of palpable hepatomegaly or splenomegaly which was not previously present.
- c. $\geq 50\%$ increase in absolute number of circulating lymphocytes over baseline with $\geq 5,000$ B cells/ μ L.
- d. Transformation to a more aggressive histology (Richter syndrome) documented with biopsy.
- e. PLT or HGB decrease $\geq 50\%$ from baseline secondary to CLL/SLL.

9.2 Active HBV infection or hepatitis.

9.3 Patient request.

9.4 General or specific changes in the patient's condition render the patient unacceptable for further treatment in the judgment of the investigator

9.5 Unacceptable toxicity that in the opinion of the investigator makes it unsafe to continue therapy.

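### Section 5 gives one ungraded half-rate restart for reactions in infusions 1 and 2 and does not say whether Section 3's graded rules (12 mL/hr after grade 3, no resumption after grade 4) apply

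*Combined protocol and SAP*

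**What the plan says.** **Section 5.0, first 300 mg and first 1000 mg infusions.** "If an infusion reaction develops, the infusion should be temporarily slowed or interrupted". Then: "Upon restarting, the infusion rate should be half of the infusion rate at the time the infusion was paused". An infusion paused at 12 mL/hr restarts at 12, and later increases are left to the investigator. No grade is named, and the reaction need not have improved to a stated level before restarting.

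**Section 5.0, subsequent infusions.** Grade sets the starting rate of the next infusion: after a grade 3 or higher infusion-associated event, it begins at 12 mL/hr on Table 2. There is no rule for restarting within infusion 3 or later. The section closes by leaving toxicity management, including slowing the infusion, to the treating physician.

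**Section 3.0, Dose Adjustments.** Grades 1 and 2 resume at half the previous rate. For grade 3 the infusion is interrupted and, "if reaction resolves or remains less than or equal to grade 2, resume infusion at a rate of 12 mL/hr". For grade 4: "infusion reaction, grade 4: discontinue the infusion and do not resume".

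**The link between the two.** Section 3 is headed as background. Its adult dosing entry notes "This dosing schedule refers to the pivotal trial" and sends the reader to Section 5 for this trial's schedule. The note is not repeated at Dose Adjustments, and Section 5 neither adopts nor sets aside that list.

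**The concern.** For the same event, a grade 3 reaction in one of the first two infusions, the protocol contains two restart rates. The one in the treatment plan is the faster. Section 3's Precautions say that serious infusion reactions occur especially in the first two infusions, which is where the texts differ.

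Section 5 is also uneven in itself. A grade 3 reaction sends the patient back to 12 mL/hr at the next visit, yet the same infusion may be restarted at up to 100 mL/hr.

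The toxicity monitoring rule in Section 10.0 is no backstop. It counts only drug-related toxicity of grade 4 or higher that lasts more than a week. A grade 3 reaction never counts, nor does a grade 4 reaction that settles within the week. Patient safety during the infusion therefore rests on the written restart instruction and on the physician's judgment.

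**Working it through.** **Inputs**
- Table 2 rates for infusions 1 and 2: 12, 25, 50, 100 and 200 mL/hr (Section 5).
- Concentrations in this trial: 0.3 mg/mL (300 mg) and 1.0 mg/mL (1000 mg) (Section 5).
- Section 3 grade 3 restart: 12 mL/hr. Section 3 equates 12 mL/hr with 3.6 mg/hr on dose 1 and 24 mg/hr on dose 2.

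**Reproducing Section 3's drug rates.** Dose 1: 12 × 0.3 = 3.6 mg/hr, as printed. Dose 2: 2000 mg in 1000 mL is 2 mg/mL, and 12 × 2 = 24 mg/hr, as printed. The first 300 mg infusion therefore has the same concentration in both texts. The second infusion here is half as concentrated as the one Section 3 describes.

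**Restart after a grade 3 reaction.** The Section 5 restart is the paused rate ÷ 2, except that 12 stays at 12. Volume ratio = Section 5 restart ÷ 12.

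| Paused at (mL/hr) | Section 5 restart (mL/hr) | Section 3 restart (mL/hr) | Volume ratio | Infusion 1, mg/hr (ratio) | Infusion 2, mg/hr (ratio) |
|---|---|---|---|---|---|
| 12 | 12 | 12 | 1.0 | 3.6 vs 3.6 (1.0) | 12 vs 24 (0.5) |
| 25 | 12.5 | 12 | 1.04 | 3.75 vs 3.6 (1.04) | 12.5 vs 24 (0.52) |
| 50 | 25 | 12 | 2.1 | 7.5 vs 3.6 (2.1) | 25 vs 24 (1.04) |
| 100 | 50 | 12 | 4.2 | 15 vs 3.6 (4.2) | 50 vs 24 (2.1) |
| 200 | 100 | 12 | 8.3 | 30 vs 3.6 (8.3) | 100 vs 24 (4.2) |

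The last column compares Section 5's drug rate with the drug rate Section 3 itself gives for dose 2. By volume, the texts differ materially only after pauses at 50 mL/hr or more. In drug per hour on infusion 2, they differ materially only after pauses at 100 or 200. For grades 1 and 2 both texts halve the rate, so there is no conflict.

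**Extra infusion time if grade 3 restarts at 12 mL/hr, infusions 1 and 2.** Assume 30-minute steps up Table 2 and at least 93.5 mL left to give. From 12 mL/hr, the steps 12, 25, 50 and 100 deliver 6 + 12.5 + 25 + 50 = 93.5 mL in 2 h, then 200 mL/hr. Extra time = difference in stepping time − (difference in volume delivered ÷ 200).
- Paused at 50: the half-rate route gives 87.5 mL in 1.5 h. Extra = 0.5 − 6/200 = 0.47 h, about 28 min.
- Paused at 100: 75 mL in 1 h. Extra = 1.0 − 18.5/200 = 0.91 h, about 54 min.
- Paused at 200: 50 mL in 0.5 h. Extra = 1.5 − 43.5/200 = 1.28 h, about 77 min.

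**The case against.** The strongest reply is that the two rules belong to different regimens. Section 3 is background, its schedule is marked as the pivotal trial's, and it uses 2000 mg doses and 100 mg prednisolone against 1000 mg and 50 mg here. Section 5 has its own premedication, rates and reaction rule. Much of this stands: Section 5 probably governs. It does not close the point. The note concerns the dosing schedule, and Section 3 also holds preparation, filter and precaution text that Section 5 does not repeat, so staff cannot treat all of it as inapplicable. If Section 5 does govern, the plan has no grade 3 limit and no grade 4 stop beyond discretion.

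A second reply is that discretion already covers the risk. Section 5 allows slowing in place of interruption, sets a rate only if the infusion is restarted, and leaves slowing to the physician. Section 3's Precautions add that "depending on the severity of the reaction, adjustment in infusion rate, interruption, and/or discontinuation of therapy is recommended". Section 9.5 allows removal for "Unacceptable toxicity that in the opinion of the investigator makes it unsafe to continue therapy". This also stands, as permission and not as a requirement.

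Three stronger readings are tempting, and the documents do not support them:
- *An eightfold faster drug rate in both infusions.* In drug per hour, 8.3 holds only for the 300 mg infusion; for infusion 2 the maximum is about 4.2.
- *The plan compels a fast restart after grade 3 or 4.* It does not require a restart at all.
- *A predictable number of patients is exposed.* Section 3 reports infusion complications of 44% and 29% for the first and second infusions. In 42 patients that would be 18.5 + 12.2, or about 31 reactions. But those figures carry no grade, come with a different dose and premedication, and say nothing about the rate at the pause.

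**Conclusion.** The point holds as an unresolved difference between the treatment plan and the protocol's own drug-safety text. It is confined to grade 3 reactions in infusions 1 and 2 paused at 50 mL/hr or more. Two gaps sit beside it: Section 5 has no grade 4 stop and no restart rule from infusion 3 onward.

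By volume, the Section 5 restart is 2.1 to 8.3 times Section 3's. In drug per hour it is 2.1 to 8.3 times for the 300 mg infusion and about 1.04 to 4.2 times for infusion 2. The infusion 2 range rests on taking Section 3's 24 mg/hr as the comparator; the whole comparison assumes that a physician applies Section 5 as written.

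The number of patients affected cannot be derived from the documents and may be small. A reader might infer a consequence for the trial's inference; there is none, since no analysis, sample size or stopping boundary depends on the restart rate. It is a patient-safety clarification that should be made.

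**What to change.** Amend Section 5 to state, for all infusions:
- **Grade 1 or 2:** restart at half the paused rate, or at 12 mL/hr if paused at 12.
- **Grade 3:** restart at 12 mL/hr only once the reaction has resolved or is grade 2 or lower. Then escalate every 30 minutes as tolerated, up to the maximum of the applicable table: 200 mL/hr under Table 2, 400 mL/hr under Table 3.
- **Grade 4:** discontinue that infusion and do not resume it.

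Add a sentence saying that Section 5 governs over Section 3, Dose Adjustments.

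The cost is one wording amendment, with no extra patients or procedures. In infusions 1 and 2, a grade 3 reaction paused at 50 to 200 mL/hr would mean about 28 to 77 more minutes of infusion. From infusion 3 onward the delay cannot be measured against the present plan, because there is no restart rule to compare with. A patient with a grade 4 reaction would forgo the rest of that dose.
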